#### **5.4.5 Termination of Study**

The National Institute of Allergy and Infectious Diseases (NIAID), or each site's IRB of record may discontinue the study at any time. Should the study be discontinued prior to completion, any subjects on study will complete study visits, if medically appropriate, but no new subjects will be enrolled.

Although the study Sponsor has every intention of completing this study, it reserves the right to terminate this study at any time for clinical or administrative reasons. Reasons for termination include, but are not limited to, study closure due to DSMB review and recommendation and at the discretion of DMID.

## 6 STUDY INTERVENTION/INVESTIGATIONAL PRODUCT

### 6.1 Study Product Description

#### Azithromycin

Azithromycin, USP is an azalide antibiotic and is derived from erythromycin. Azithromycin as the dehydrate, is a white crystalline powder with a molecular formula of  $C_{38}H_{72}N_2O_{12} \cdot 2H_2O$  and a molecular weight of 785.0.

#### VIDAS® B.R.A.H.M.S Procacitonin Test

The [VIDAS® B.R.A.H.M.S PCT](#) is an automated test for use on the VIDAS instruments for the determination of human procalcitonin in human serum or plasma using the Enzyme-Linked Fluorescent Assay (ELFA) technique. The [VIDAS® B.R.A.H.M.S PCT](#) is intended for use in conjunction with other laboratory findings and clinical assessments to aid in the risk assessment of critically ill patients on their first day of ICU admission for progression to severe sepsis and septic shock. It is also used in conjunction with other laboratory findings and clinical assessments to aid in decision making on antibiotic therapy for patients with suspected or confirmed LRTI, or patients with suspected or confirmed sepsis.

#### 6.1.1 Acquisition

##### 6.1.1.1 Azithromycin and Placebo

Over-encapsulation, packaging, and labeling of study drug will be performed according to applicable regulatory requirements. All study drugs (azithromycin and placebo) will be distributed through the DMID Clinical Materials Services (CMS, Fisher BioServices).

Study product (azithromycin and matching placebo) will be shipped from the DMID CMS to the study sites upon request and approval by DMID.

##### 6.1.1.2 VIDAS® B.R.A.H.M.S Procalcitonin Research Test Kits

The VIDAS® B.R.A.H.M.S PCT Kits for the trial will be provided by bioMerieux and distributed through the DMID Clinical Materials Services (CMS). The kits will be manufactured following current good manufacturing practices (cGMP) and labeled as investigational use only (IUO). The kits will be shipped to CMS under controlled condition defined by the package insert (also refer as IFU) with tracking documents. CMS will be responsible for maintaining the kits under proper condition, distributing the kits to the testing labs, and controlling the inventory and accountability after receiving products from bioMerieux. The VIDAS® B.R.A.H.M.S PCT will be shipped from the DMID CMS to the study sites upon request and approval by DMID.

### **6.1.1.3 VIDAS® 3 Platform Research Lab**

The VIDAS® 3 platform will be provided, installed and qualified by field service engineers (FSE) from bioMerieux prior to initiation of the clinical evaluation. The participating laboratory sites will be CLIA-certified laboratories (or equivalent) capable of performing VIDAS® B.R.A.H.M.S PCT testing on VIDAS®3 platform and reporting the results to clinical sites within turnaround time defined in this trial.

Annual maintenance will also be provided by bioMerieux. The general maintenance will be performed by the testing laboratory per the user's manual. After the completion of the trial, the instruments will be deinstalled by bioMerieux FSE and shipped back to bioMerieux

### **6.1.1.4 VIDAS® B.R.A.H.M.S Procalcitonin Clinical Test Kits**

With prior approval of DMID, CLIA certified clinical laboratory services for VIDAS® B.R.H.A.M.S. procalcitonin measurement may be used. Test kits will be obtained through routine clinical laboratory procedures. Results will be reported to the study team within the protocol specified time frame.

## **6.1.2 Formulation, Packaging, and Labeling**

### **6.1.2.1 Azithromycin and Placebo**

Azithromycin will be supplied as 250 mg over encapsulated tablets. Each capsule will contain one-250mg azithromycin tablet and an inert filler.

Placebo will be supplied as matching capsules containing an inert filler. In order to maintain the blind, the capsules are the same size, weight, and color as the capsules containing Azithromycin tablets.

Additional details will be provided in the protocol-specific MOP.

All study products will be packaged in identical containers each containing 6 capsules. Each container will also be labeled in compliance with applicable regulatory requirement, including the FDA- required cautionary statement "*Caution-New drug-Limited by Federal (or United States) Law to Investigational Use Only.*"

### **6.1.2.2 VIDAS® B.R.A.H.M.S Procalcitonin Test Kits**

The VIDAS® B.R.A.H.M.S. PCT kit consists of 60 tests. The contents of the kit are 60 PCT strips (each strip consists of 10 wells), 60 ready to use solid phase receptacles (SPR) coated with mouse monoclonal anti-human procalcitonin immunoglobulins, 2 lyophilized PCT controls C1 and C2, 2 lyophilized PCT calibrators S1 and S2 and a master lot entry card (MLE).

### **6.1.3 Product Storage and Stability**

#### **6.1.3.1 Azithromycin and Placebo**

Azithromycin and placebo capsules must be stored at 20°C to 25°C (68°F to 77°F); excursions between 15°C and 30°C (59°F and 86°F) are permitted. [See USP Controlled Room Temperature].

#### **6.1.3.2 VIDAS® B.R.A.H.M.S Procalcitonin Test Kits**

The VIDAS® B.R.A.H.M.S. PCT kit must be stored at 2°C to 8°C (35° to 46°F). DO NOT Freeze reagents, with the exception of calibrators and controls after reconstitution. All unused reagents must be stored at 2°C to 8°C (35° to 46°F). Additional information and details can be found in the package insert.

## **6.2 Dosage, Preparation and Administration of Study Intervention/Investigational Product**

### **6.2.1 Azithromycin and Placebo**

Azithromycin 500 mg or placebo (administered orally as two 250 mg capsules or two matching placebo capsules) as a single dose within 24 hours of randomization, followed by Azithromycin 250 mg or placebo (administered orally as one 250 mg capsule or one matching placebo capsule) once daily for 4 days (Day 2 through Day 5).

Capsules should be maintained as dispensed and not scored, cut, crushed, or otherwise divided for ease of swallowing. The capsules will be administered with water sufficient for the subject to swallow the required number of capsules.

## **6.3 Modification of Study Intervention/Investigational Product for a Subject**

No modifications of study product are planned at this time. If a subject experiences any individual halting rule, as defined in Section 9.5.2, they will be taken off of the study drug.

## **6.4 Accountability Procedures for the Study Intervention/Investigational Product(s)**

### **6.4.1 Azithromycin and Placebo**

After receipt of the study product, the site Principal Investigator (PI) is responsible for distribution and disposition of these study products, and has ultimate responsibility for drug accountability. As this is a blinded study, the site PI will delegate this responsibility to the unblinded site pharmacist. Study product records must be maintained and document logs of receipt, accountability, and storage temperature conditions. These study product accountability and dispensing logs must be maintained in the study file. Upon completion of the study and after the final monitoring visit, unused study product that has not been dispensed will be retained until monitored and released for disposition as per the Sponsor.

### **6.4.2 VIDAS® B.R.A.H.M.S. Procalcitonin Test Kits**

After receipt of the VIDAS PCT kits, the site PI is responsible for distribution and disposition of these kits, and has the ultimate responsibility for PCT kits accountability. The site PI will delegate this responsibility to the site CLIA certified laboratory personnel.

VIDAS PCT kits must be maintained and document logs of receipt, accountability, and storage temperature conditions. These kit accountability logs must be maintained in the study file. Upon completion of the study and after the final monitoring visit, unused kits will be retained until monitored and released for disposition as per the Sponsor.

When a clinical laboratory performs procalcitonin testing, standard operating procedures as defined by CLIA guidelines will be used to document the receipt, accountability, and storage of PCT kits.

### **6.4.3 VIDAS® Platform**

The normal maintenance of the VIDAS® platform will be performed and documented by the laboratory. Annual maintenance of the VIDAS® 3 instruments will be provided by bioMerieux. For sites where PCT is measured in a CLIA-certified clinical laboratory, maintenance will be performed according to standard operating procedures as defined by CLIA.

## **6.5 Assessment of Subject Compliance with Study Intervention/Investigational Product**

The investigator will maintain records documenting all study products (azithromycin or placebo) administered to each subject for the entire study period. Subjects will be asked to complete a memory aid and bring their study product containers to Study Visit 3. The memory aid will be used to record daily study product taken, unscheduled medical visits,

concomitant medications, temperature, solicited events, and specified symptoms. The study coordinator/investigator will document any missed doses of study product and provide counseling per study sites' routine procedures to promote compliance with study product. The information on the memory aid will be recorded on a source document, but the memory aid will not be collected from the subject. If a subject's memory aid is not available, study product compliance will be obtained by subject interview. In addition, the subject will be reminded to bring the study product container for the purpose of maintaining drug accountability. If the study product container is available, product compliance will be verified by checking that the number of remaining pills (if any) is consistent with the memory aid review. The study coordinator/investigator will record how study product compliance information was obtained including options for interview, memory aid review, and study product container verification. Empty study product bottles will be discarded in accordance with site standard operating procedures.

## **6.6 Concomitant Medications/Treatments**

Administration of any medications, therapies, or vaccines including dose and frequency, will be recorded on the appropriate data collection form. Concomitant medications will include all current medications and medications taken within 30 days prior to signing the informed consent form. Prescription and over-the-counter drugs will be included, as well as herbals, vitamins, and supplements. Any symptomatic treatment received on the day of/during the enrollment visit will not be recorded unless it is a non-study systemic antibiotic.

Subjects will also be asked specifically about the use of non-study systemic antibiotics following enrollment and through the last study visit, but no concomitant medications other than antibiotics will be recorded after enrollment.

Use of new medication should prompt evaluation for the presence of a new diagnosis of chronic medical disease or condition.

Medications that might interfere with the evaluation of the study product or may compromise subject safety should not be used during the study. Medications in this category include the prohibited medications per the Subject Exclusion Criteria (see Section 5.2). In addition, the site principal investigator or appropriate sub-investigator may identify other medications that should not be used due to a risk to subject safety.

## **7 STUDY SCHEDULE**

### **7.1 Screening**

Each study site will determine the most efficient procedures to identify potentially eligible subjects from primary care clinics, urgent care centers, and emergency departments (EDs) affiliated with the study clinical trial centers. Providers will be informed about the study and provided with a TRAP-LRTI information pamphlet summarizing the study design and subject eligibility criteria. Providers may also be asked to alert their patients about their practice's participation in the TRAP-LRTI study, instructing them that study personnel may contact them to discuss potential research opportunities.

The identification of potentially eligible subjects will vary by site and practice setting and will include direct communication with providers, review of clinical intake logs, and electronic health record (EHR) alerts that automatically screen for LRTI cases from medical records.

Suspected LRTI will be defined as specified in eligibility criteria #1.

Once a potentially eligible subject with suspected LRTI is identified, study staff will coordinate with clinical providers based on local site practice. Study staff will then approach the eligible subject to explain the study protocol and describe the inclusion/exclusion criteria.

### **7.2 Enrollment/Baseline- Visit 1 (Day 1)**

At the Enrollment Visit, study staff will obtain written informed consent from the subject for the primary study and for future use of samples and data. Declination to participate in collection of future use samples will not affect participation in the primary study. After the subject has had the opportunity to ask questions and has signed the informed consent document, the following activities will be performed:

- Eligibility criteria for enrollment will be reviewed;
- An assessment of LRTI signs and symptoms will be made
- Blood samples will be obtained and used for PCT measurement and future use (if consented).

Additional information will be obtained from the subject as follows:

- A complete medical history and sociodemographic data will be obtained by direct interview of the subject and medical record review
- A physical examination will be performed to determine general appearance and focused HEENT, neck, cardiopulmonary, and abdominal examinations; vital signs, including

temperature, blood pressure, pulse rate, respiratory rate, and pulse oximetry (obtained clinically).

*\* Note: physical examinations may be performed by physicians, advanced practice nurses, physician assistants, or nurses obtained either by study investigators or as part of clinical care.*

- Concomitant medications taken in the last 30 days will be recorded based on subject report or medical record review (see section 6.6. for details)
- A nasopharyngeal swab specimen will be collected for respiratory viral testing and banking.

The PCT value is expected to be available to the investigator within 2 hours of the blood draw. The study team will not report PCT results to the subject or the provider. Once the subject's PCT value is available, subjects with a PCT > 0.25 ng/mL will not be randomized. Providers will be notified that the patient will not be randomized and therefore, the treating provider should make treatment decisions.

Subjects with PCT ≤ 0.25 ng/mL will be randomized 1:1 to receive oral azithromycin or placebo and the following procedures will be performed:

- Study product will be dispensed and study staff will review the study product with the subject and review the study product storage and dosing instructions. Preferably, the study staff will witness the subject take the first dose of study product, which will be recorded on the memory aid.
- Subjects will be provided with a memory aid and other study-related materials to record daily temperature, solicited events, specified symptoms, concomitant medications, daily dose administration, and any unscheduled medical visits. Study staff will instruct the subject to complete the memory aid in order to assess adherence and to bring the aid and the medication bottle with them to Visit 3. Study staff will also train subjects on proper completion of the memory aid used to assess specific, solicited events.

## 7.3 Follow-up Visits for Randomized Subjects

### 7.3.1 Visit 2 (Day 3 + 1 day)

Study subjects will be evaluated on Day 3 via telephone. During the telephone call, study personnel will assess LRTI signs and symptoms. If the study team identifies concerns about worsening of clinical status, the subject will be advised to seek care from his/her provider or the nearest ER if indicated. Study staff will assist in facilitating the follow up appointment. This includes signs or symptoms of pneumonia (including fever, increased difficulty breathing, or increased/worsening cough) or development of a severe solicited event. The study staff will also review any new or changed concomitant medications with the subject. UADEs will be recorded if any occur.

Study staff will also ask about medication compliance and any solicited adverse events.

### **7.3.2 Visit 3 (Day 5 + 3 days)**

The visit on Day 5 will represent the primary outcome assessment and will include an assessment of LRTI signs and symptoms. Also at Day 5, blood samples will be collected for repeat PCT testing. To permit evaluation of the secondary RADAR outcomes, all clinical parameters pertinent to the RADAR assessment will be ascertained at this time. This will be an in-person visit conducted at the study site. This visit can also be conducted in the subject's home.

Prior to this visit, study staff will make a preliminary assessment of the clinical response using the electronic health record to determine whether any of the following events have occurred after randomization and anticipated receipt of at least one dose of study agent.

- The subject had a medically attended visit to an ED, urgent care, or clinic;
- The subject was hospitalized during a separate clinical encounter following the enrollment encounter
- The subject received non-study, systemic antibiotic therapy

At the Day 5 visit, study staff will complete the following procedures:

- Assessment of clinical improvement including:
  - Review and collection of vital signs
  - Assessment and grading of LRTI symptoms
  - Occurrence of any medically attended visits
  - Receipt of any non-study systemic antibiotics
- Abbreviated physical examination to include general appearance and focused HEENT, neck, cardiopulmonary, and abdominal examinations;
- Review of the subject's memory aid
- Assess and record any solicited events and UADEs
- Review of memory aid and study product bottle (if available) to assess treatment compliance
- Obtain blood sample for PCT testing
- Review of study product bottle for drug accountability, if available;

If the subject develops signs or symptoms of pneumonia (including fever, increased work of breathing, increased/worsening cough, or new pulse oximetry reading  $\leq 90\%$ ) or develops a severe solicited event, the subject will be referred to his/her primary care provider or local urgent care center/ED. Study staff will assist in facilitating the follow up appointment. The study

staff will share all pertinent information related to the study with the treating clinician including treatment arm assignment if clinically indicated as determined by the treating clinician and the study's site investigator.

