### **7.3.3 Visit #4 (Day 11 + 3 days)**

Study subjects will be evaluated on Day 11 via telephone. Secondary and exploratory outcome measures will be assessed at this follow up. Study staff will complete the following procedures:

- Assessment of clinical improvement including:
  - Review and collection of temperature
  - Assessment and grading of LRTI symptoms
  - Occurrence of any medically attended visits
  - Receipt of any non-study systemic antibiotics
- Review of the subject's memory aid
- Assess and record any solicited events and UADEs

If the subject develops signs or symptoms of pneumonia (including fever, increased work of breathing, or increased/worsening cough) or develops a severe solicited event, the subject will be referred to his/her primary care provider or local urgent care center/ED. Study staff will assist in facilitating the follow up appointment. The study staff will share all pertinent information related to the study with the treating clinician including treatment arm assignment if clinically indicated as determined by the treating clinician and the study's site investigator.

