### **7.3.4 Visit # 5 Final Visit (Day 28 ± 2 days)**

Study subjects will be evaluated on Day 28 via telephone. Secondary outcome measures will be assessed at this follow up. Study staff will complete the following procedures:

- Assessment of clinical improvement including:
  - Review and collection of temperature
  - Assessment and grading of LRTI symptoms
  - Occurrence of any medically attended visits
  - Receipt of any non-study systemic antibiotics
- Assess and record any UADEs

If the subject develops signs or symptoms of pneumonia (including fever, increased work of breathing, or increased/worsening cough) or develops a severe solicited event, the subject will be referred to his/her primary care provider or local urgent care center/ED. Study staff will assist in facilitating the follow up appointment. The study staff will share all pertinent information

related to the study with the treating clinician including treatment arm assignment if clinically indicated as determined by the treating clinician and the study's site investigator.

The study staff will also review any new or changed con-commitment medications with the subject. A review of the medical record will also be done to recording results of clinical laboratory evaluations as specified in Section 8.2.1.

The exact date of the follow-up visit will be documented throughout the study.

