## **7.4 Follow-up for Non-randomized Subjects**

### **7.4.1 Visit #5N (Day 28+7)**

At enrollment, subjects with a PCT level > 0.25 ng/ml will still have data and samples collected but they will not be randomized. Their charts will be reviewed through 28 days after enrollment in order to support future use research. This may include recording the results of clinical laboratory evaluations as specified in Section 8.2.1. Review of medical history will be performed to determine whether medically attended visits or receipt of systemic antibiotics have occurred.

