Solicited event assessments will include an assessment of solicited events occurring from the time of enrollment through Visit 4 (Day 11+3 days). All subjects will be instructed to complete a subject memory aid from the time of enrollment through Visit 4 (Day 11+3 days). Subject memory aids will be reviewed with the subject for any discrepancies or missing data and data will be recorded by study coordinators.

*\* Note: physical examinations may be performed by physicians, advanced practice nurses, physician assistants, or nurses.*

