- If a subject did not complete D11V and had no MAV submitted, then MAV or Hospitalization for persistent or worsening LRTI at D11V is missing.
- Otherwise, if a subject completed D11V but had no MAV submitted then MAV or Hospitalization for persistent or worsening LRTI at D11V is absent.

Similar derivations will be used for D28V by replacing D11V by D28V.

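### For randomised subjects a health-record search for visits, hospitalisations and non-study antibiotics is specified only before Visit 3, so later events that go unreported are analysed as non-events

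*Protocol*

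**What the plan says.** **Up to Visit 3.** Protocol 7.3.2 has staff check for three kinds of event before the visit, "using the electronic health record to determine whether any of the following events have occurred after randomization": a medically attended visit, a hospitalisation separate from the enrolment encounter, and non-study systemic antibiotics. The in-person visit then asks about visits and antibiotics again.

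**Visit 4.** Protocol 7.3.3: "Study subjects will be evaluated on Day 11 via telephone". The call covers visits and antibiotics and includes "Review of the subject's memory aid". Protocol 7.2 lists the memory aid's contents, among them "concomitant medications, daily dose administration, and any unscheduled medical visits". Protocol 8.1 has subjects keep it from enrolment to Visit 4.

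**Visit 5.** Protocol 7.3.4 is again a telephone contact covering the same events, with no memory aid. It adds: "A review of the medical record will also be done to recording results of clinical laboratory evaluations", with a pointer to Section 8.2.1. It names no search for visits, admissions or antibiotics.

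**Non-randomised subjects.** Protocol 7.4.1: "Their charts will be reviewed through 28 days after enrollment". That review does look for medically attended visits and systemic antibiotics.

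**SAP coding.** SAP 6.5.2.3 treats the event as present if a qualifying MAV form exists, and as absent if the visit was completed and no form was submitted. For the remaining case: "If a subject did not complete D11V and had no MAV submitted, then MAV or Hospitalization for persistent or worsening LRTI at D11V is missing". The same rules apply at Day 28.

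**The concern.** One kind of event is reported cumulatively to Day 5, Day 11 and Day 28 and is a component of clinical improvement at all three visits, but the record is searched for it only at the first. After that, a visit or antibiotic course that the subject does not mention leaves no form, and the SAP turns the absence of a form into a negative finding.

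At stake are the Day 11 and Day 28 secondary comparisons: return visits, emergency department visits, hospitalisations, days of antibiotic use, and the supportive non-inferiority analyses of clinical improvement. In a trial that asks whether an antibiotic can be withheld, late care-seeking and rescue antibiotics are outcomes that readers will look for. The omission also stands out because a 28-day chart review for these events is already done in the cohort that enters no treatment comparison.

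**Working it through.** The documents give no event rate, detection sensitivity or power for these comparisons, so there is no planned figure to reproduce.

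**Step 1. Source of information by interval** (Protocol 7.2 to 7.4, 8.1 and Appendix A; visit windows from SAP 3.3.1)

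| Interval | Record search for these events | Self-report |
|---|---|---|
| Randomisation to Visit 3 (Day 5–8) | Yes | Visit 2 call, in-person Visit 3, memory aid |
| Visit 3 to Visit 4 (Day 11–14) | None specified | Telephone and memory aid |
| Visit 4 to Visit 5 (Day 26–30) | None; record opened for laboratory results | Telephone alone |
| Non-randomised, to Day 28 | Yes | None; subject not contacted |

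The telephone-only stretch runs from 26 − 14 = 12 to 30 − 11 = 19 days.

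**Step 2. Effect of equal misses.** Assume each arm detects the same share *s* of true events, with no false positives. Blinding makes this plausible but does not guarantee it. The observed rate is *s* × the true rate. Then:

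- risk difference = *s* × (p₂ − p₁), which shrinks in proportion;
- risk ratio = p₂/p₁, unchanged;
- odds ratio = [s·p₂/(1 − s·p₂)] ÷ [s·p₁/(1 − s·p₁)], which moves slightly towards the risk ratio.

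The rates below (azithromycin vs placebo) and the values of *s* are assumptions. The 280 per arm is the ATP-5 target (Protocol 5), because ATP-11 and ATP-28 sizes are not given. Power is exact, for a two-sided Fisher test at 0.05.

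| True rates | s | Risk difference (points) | Odds ratio | Fisher power |
|---|---|---|---|---|
| 2% vs 4% | 1.0 / 0.8 / 0.6 | 2.0 / 1.6 / 1.2 | 2.042 / 2.033 / 2.025 | 21% / 15% / 11% |
| 5% vs 10% | 1.0 / 0.8 / 0.6 | 5.0 / 4.0 / 3.0 | 2.111 / 2.087 / 2.064 | 56% / 44% / 33% |
| 10% vs 18% | 1.0 / 0.8 / 0.6 | 8.0 / 6.4 / 4.8 | 1.976 / 1.935 / 1.897 | 75% / 63% / 48% |

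**Step 3. Allow for cumulative counting.** The table applies *s* to all events, which is the worst case. Counts run from randomisation, so events found by Visit 3 are kept. If a share *f* of the excess is already captured then, the observed excess is the true excess × [f + (1 − f)s]. For an assumed 4-point excess and *s* from 0.6 to 0.9:

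- f = 0 gives 4 × 0.6 = 2.4 to 4 × 0.9 = 3.6 points;
- f = 0.5 gives 4 × 0.80 = 3.2 to 4 × 0.95 = 3.8 points.

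**Step 4. Match to the planned analyses.**

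- Day 11 and Day 28 visits, emergency department visits and hospitalisations use odds ratios and Fisher's test in ATP-11 and ATP-28 (SAP 8.2.6). The loss is mainly power.
- The exploratory Day 11 event analysis uses risk differences (SAP 8.3.5). These shrink as shown.
- Clinical improvement at Days 11 and 28 uses a difference in proportions (SAP 8.2.2 and 8.2.3). Only the part contributed by events shrinks, and only through subjects who do not already fail on symptoms.

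**The case against.** The strongest reply is that the core method does not change. The check before Visit 3 is preliminary, and the formal assessment asks about visits and antibiotics at Visits 3, 4 and 5 alike. SAP 6.5.5 also plans site queries to make antibiotic records complete and consistent with the medically attended visit records. Self-report can capture care outside the site's system, which the record cannot. For non-randomised subjects the chart replaces an interview. Nothing in the documents shows that the record is the more sensitive source.

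Much of this stands. The record search is a second source that lapses, not the only one. But the planned queries compare records within the database, and no search of the health record is specified for Days 11 or 28. An event that no one reported would therefore generate no inconsistency to query.

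A reader might infer several stronger things that the documents do not support:

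- **That everything from Day 6 to Day 28 rests on a telephone call.** The memory aid records unscheduled visits through Visit 4, and Visit 3 itself may fall as late as Day 8.
- **That the Day 11 and Day 28 event comparisons are biased towards no difference.** With equal misses the planned odds ratios barely move. With unequal misses the bias could go either way.
- **That a treated visit in a subject not reached by telephone is necessarily lost.** SAP 6.5.2.3 codes a qualifying MAV form as present whether or not the visit was completed. What is missing is a step that would generate the form.
- **That the intensive-care halting rule depends on the Day 28 call.** Protocol 9.5.1 describes ongoing safety review and does not make that link.

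**Conclusion.** The point holds as a gap in how secondary events are ascertained. After Visit 3, no record search for visits, hospitalisations or non-study antibiotics is specified for randomised subjects, and at a completed visit an unreported event is coded as absent.

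If misses are equal in the two arms, the consequences are lower power for the Day 11 and Day 28 event comparisons, almost unchanged odds ratios, and smaller risk differences. Any event contribution to the Day 11 and Day 28 non-inferiority differences also shrinks, and there shrinkage favours non-inferiority. The size cannot be known from the documents: every rate and sensitivity above is assumed, and events found by Visit 3 limit the loss.

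The Day 5 primary analysis is not affected, and SAP 8.1.1 rests the non-inferiority conclusion on that analysis alone. This is a cheap improvement to secondary outcomes, not a threat to the trial's main conclusion.

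**What to change.** In Protocol 7.3.4 and Appendix A, widen the Visit 5 record review to cover medically attended visits, hospitalisations and non-study systemic antibiotics from randomisation through Day 28. Do it for every randomised subject, including those not reached by telephone, subject to consent. Record dates, so that Day 11 status can be updated using only events that had occurred by then. Enter what is found on the MAV and concomitant medication forms; the existing SAP 6.5.2.3 rule will then code a qualifying event as present. Optionally, repeat the Visit 3 check at Visit 4.

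The cost is protocol wording and a few minutes of staff time per subject. The record is already opened at Visit 5, and a Day 28 review for visits and antibiotics already exists for non-randomised subjects. Care outside the site's record will still be missed, so the telephone questions should stay.
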